## 9 HANDLING OF MISSING VALUES

No imputation of missing values will be carried out and the analyses will use a complete-case approach. The eCRF setup allows missing information for a number of variables to be included as ‘not recorded’ or ‘not stated’ options, and numbers of patients in these categories will be reported in descriptive statistics where appropriate. Descriptive statistics reported for continuous variables will include the numbers of patients with non-missing data per variable. For time-to-event analyses, the numbers of uncensored (at-risk) individuals will be reported at each timepoint.

For eCRF Q2 (‘Patient’s month and year of birth’), date of the month will not be recorded, and for eCRF Q10 (‘Date of locally advanced or metastatic UC diagnosis’), date of the month can be entered as unknown. For both of these variables, the 15th date of the month will be used to complete the full date as needed.

For eCRF Q4 (‘Date of initial diagnosis of urothelial carcinoma’), partial dates are allowed to be recorded where either date only is missing, or where date and month are both missing. Where only month and year are recorded, the date will be analysed as the 15th date of that month. Where only year is recorded, the date will be analysed as the 30th June of that year. Since this data is only used to calculate (i) age (in years) at first diagnosis, and (ii) time between initial diagnosis and locally advanced/metastatic diagnosis, this level of precision is expected to be sufficient.

PFIZER CONFIDENTIAL

CT24-WI-GL03-RF03 0.2 *Non-Interventional Statistical Analysis Plan For Secondary Data Collection*  
*Study 01-Jun-2020*  
Page 28 of 34

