### **Inclusion Criteria**

Each inclusion criterion is indicated explicitly on the eCRF as a yes/no indicator variable. Patients must meet all the following inclusion criteria to be eligible for inclusion in the study:

- Patients with a diagnosis of locally advanced or metastatic UC, either de novo or relapsed, prior to or on the date of avelumab treatment initiation
- Patients received 1L platinum-based chemotherapy and had stable disease, partial response, or complete response to this treatment recorded prior to the date of avelumab treatment initiation
- Patients received avelumab as indicated as a monotherapy for the first-line maintenance treatment of adult patients with locally advanced or metastatic UC who are progression-free following platinum-based chemotherapy
- Patients aged  $\geq 18$  years on the date that they commenced avelumab
- Patients whose hospital records are available for review

PFIZER CONFIDENTIAL

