ECOG performance status at locally advanced or metastatic diagnosis	Clinical characteristic	At date of locally advanced or metastatic cancer diagnosis (or if not available, at date of first diagnosis)	
As recorded in eCRF Q19:
 
 
• 0 = Fully active, able to carry on all pre-disease performance without restriction
 
• 1 = Restricted in physically strenuous activity but ambulatory and able to carry out work of a light or sedentary nature, e.g., light housework, office work
 
• 2 = Ambulatory and capable of all self-care but unable to carry out any work activities. Up and about more than 50% of waking hours
 
• 3 = Capable of only limited self-care, confined to bed or chair more than 50% of waking hours
 
• 4 = Completely disabled. Cannot carry on any self-care. Totally confined to bed or chair
 
• Not recorded
 

De novo or newly relapsed	Clinical characteristic	At date of locally advanced or	
As recorded in eCRF Q15:
 
 
• De novo disease
 

PFIZER CONFIDENTIAL

CT24-WI-GL03-RF03 0.2 *Non-Interventional Statistical Analysis Plan For Secondary Data Collection*  
*Study 01-Jun-2020*  
 Page 20 of 34

		metastatic cancer diagnosis	
 
• Newly relapsed disease
 

Site of metastases at locally advanced or metastatic diagnosis	Clinical characteristic	At date of locally advanced or metastatic cancer diagnosis	
As recorded in eCRF Q16:
 
 
• Lymph nodes
 
• Bone
 
• Lung
 
• Liver
 
• Peritoneum
 
• Other
 
• Not recorded
 
 
Note that free text responses can be recorded under the 'other' option on the eCRF; these patients will be counted within the patient totals for 'other'. More than one site of metastases can be selected per patient, therefore percentage of total patients reporting each site will be shown, but percentages across all categories combined will not necessarily sum to 100%.

Time from first diagnosis to locally advanced or metastatic diagnosis	Clinical characteristic	At date of locally advanced or metastatic cancer diagnosis	Time (in months) between date of first diagnosis (eCRF Q5) and date of locally advanced or metastatic diagnosis (eCRF Q10), inclusive of both dates.

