#### Analysis of continuous variables

All continuous variables will be described using the following statistics: number of observations, mean, standard deviation, median, minimum, and maximum values, first and third quartile (Q1 and Q3). The mean, median, Q1 and Q3 will be displayed to one decimal place. The standard deviation will be displayed to two decimal places.

The number of AEs, number of hospitalisations, duration of hospitalisation, and number of Accident & Emergency visits will each be used to calculate a rate per patient per year of follow-up time. This will be calculated as the total number of incident events (or total number of days hospitalisation) recorded per patient during the follow-up time divided by the total follow-up time (time at risk) per patient in years. All rate variables will be presented in the same way as for the other continuous variables.

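### Completed first-diagnosis dates are not checked against the advanced-diagnosis date, so the time between the two diagnoses can come out negative or falsely positive

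*SAP*

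**What the plan says.** SAP Section 9 allows the first-diagnosis date to be partial at two levels.

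- Day missing: "Where only month and year are recorded, the date will be analysed as the 15 th date of that month".
- Day and month missing: "Where only year is recorded, the date will be analysed as the" 30 June of that year.

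For the advanced-diagnosis date (Q10), only the day may be missing: "date of the month can be entered as unknown", and it is then set to the 15th. Section 9 justifies this by the limited use made of the first-diagnosis date (age in years, and the interval to advanced disease), and concludes that "this level of precision is expected to be sufficient".

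SAP Section 8 defines the interval as "Time (in months) between date of first diagnosis (eCRF Q5) and date of locally advanced or metastatic diagnosis (eCRF Q10), inclusive of both dates". It applies to every patient. SAP Section 10.3 summarises continuous variables by "number of observations, mean, standard deviation, median, minimum, and maximum values, first and third quartile (Q1 and Q3").

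De novo patients are eligible. The first inclusion criterion in SAP Section 6.2 reads "Patients with a diagnosis of locally advanced or metastatic UC, either de novo or relapsed, prior to or on the date of avelumab treatment initiation", and de novo or newly relapsed status is recorded at eCRF Q15. Neither document caps the completed date at Q10, treats de novo patients separately for this variable, or says what to do with a negative interval.

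**The concern.** The completion rule looks at one date only. Where first and advanced diagnosis are the same event or close together, a mid-year or mid-month substitute can land on the wrong side of the Q10 date. If it lands after Q10 the interval is negative, which is impossible. If it lands before, the patient acquires a delay that may never have happened.

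Time from first to advanced diagnosis is a planned baseline characteristic, reported with its minimum and quartiles, so one such patient can put an impossible value in the table. With no rule in the SAP, the repair would be chosen after the data are seen.

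**Working it through.** The SAP gives no figure for the precision it calls sufficient, so there is nothing of its own to reproduce. The size was found by applying its rules to every calendar day.

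**Inputs.** The completion rules (30 June, 15th) are from SAP Section 9 and the inclusive difference is from SAP Section 8. Assumptions: for a de novo patient the two diagnoses fall on the same day (the documents do not define the term); diagnoses are spread evenly over a 365-day year; a month is 30.4375 days.

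**Formula.** Interval = Q10 date - completed first-diagnosis date + 1. Two identical dates give 1 day, so 1 day is the true value for a same-day patient.

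**Year-only first date, full Q10 date, same-day diagnoses.** 30 June is day 181. With Q10 on day d, the interval is d - 181 + 1 = d - 180.

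- Range: 1 - 180 = -179 days to 365 - 180 = +185 days (-5.9 to +6.1 months).
- Negative: d = 1 to 179, so 179/365 = 49%.
- Falsely positive (over 1 day): d = 182 to 365, so 184/365 = 50%.
- Mean: 183 - 180 = 3 days, an error of +2 days.
- Quartiles in this group: -88 and +94 days. SD: about 3.5 months, where the true SD is 0.

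A leap year gives -180 to +185 days, 49% negative, mean 2.5 days.

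**Month-only first date, full Q10 date, same-day diagnoses.** With Q10 on day d of the month, the interval is d - 14.

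- Range: -13 to +17 days.
- Negative: 13 days in each of 12 months, 156/365 = 43%.
- Falsely positive: 185/365 = 51%.
- Largest error: 17 - 1 = 16 days, about half a month.

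If both dates lack the day, both become the 15th and the error vanishes. A full first date against a Q10 date set to the 15th gives -15 to +15 days, 47% negative.

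**Relapsed patients, year-only first date, true gap of g months.** With first diagnosis on day f, the interval is f + 30.4375g - 180, which is negative when f < 180 - 30.4375g.

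| True gap | Negative when | Share negative |
|---|---|---|
| 1 month | f < 149.6 | 149/365 = 41% |
| 3 months | f < 88.7 | 88/365 = 24% |
| 6 months | never (180 - 182.6 < 0) | 0% |

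**Cohort of 100.** Neither the share of de novo patients nor the frequency of year-only dates is given. Over assumed ranges (30-70% de novo, 5-50% of them year-only), the expected number of negative values among de novo patients is 100 x 0.30 x 0.05 x 0.49 = 0.7 up to 100 x 0.70 x 0.50 x 0.49 = 17. In simulation, with relapsed intervals assumed exponential with a 24-month mean, the cohort mean under the SAP rule moved by at most about 0.03 months. The median moved by 0.2 to 2.1 months when half the cohort was de novo, and by no more than about 0.25 months at 30% or 70% de novo.

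**The case against.** The damaging combination may be rare. Q10 needs at least a month and year. If the two diagnoses are one event, whoever enters Q10 already knows the month, so a year-only first date in the same patient would be odd. Year-only dates are likelier for old primary tumours in relapsed patients, where gaps of 6 months or more never give a negative value. This stands: the documents do not show that any patient is affected, and the upper end of the ranges above should not be read as a forecast.

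A completed mid-year date is also a reasonable choice for age in whole years. SAP Section 10.5 acknowledges difficulty with time-window variables and relies on training, monitoring and source data verification. The eCRF specification and data management plan are not available, so date-order checks cannot be ruled out. But a check that queries entered dates does not catch an order violation created later by the completion rule.

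A reader might infer that the reported mean is biased upward. That would follow if negatives were set to zero (mean 47 days in year-only same-day patients) or dropped (mean 93 days), but no passage says either will be done. As written, positive and negative errors nearly cancel. Those figures show only why the repair should not be left open.

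**Conclusion.** The point holds as a gap in the completion rule for one descriptive baseline variable. As written, the rule can produce impossible negative intervals and invented positive ones, by up to about 6 months for a year-only date and about half a month for a month-only date. The mean is almost unaffected (+2 days per affected same-day patient). The minimum and spread are distorted, and the quartiles may be if affected patients are numerous. The percentages rest on same-day diagnosis in de novo patients and an even spread over the year; the possibility of a negative value needs neither.

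It would be wrong to carry this over to the main results: rwOS, rwPFS and rwTTD all start at avelumab initiation and do not use the first-diagnosis date. It is a minor point, worth correcting because the correction is cheap.

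**What to change.** Add to SAP Section 9:

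- (a) If the patient is recorded as de novo (Q15) and the partial first-diagnosis date is compatible with Q10 (same year, or same month and year where the month is known), use the Q10 date. If it is not compatible, query the record and do not overwrite it.
- (b) Otherwise the completed date may not fall after Q10; use the midpoint of the possible range up to Q10.
- (c) Report the number of completed dates.

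Rule (a) is needed as well as (b). In same-day patients with year-only dates, a plain cap at Q10 still leaves a mean of about 48 days and the midpoint gives 92 days, whereas the Q10 date returns the true 1 day. The same order check should be applied when it is the Q10 day that was completed and the first date is full.

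Summarising the interval separately for de novo and newly relapsed patients would also help. Protocol Table 2 already asks for time from previous diagnosis to relapse in the latter.

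Separately, reconcile the question number for the first-diagnosis date (Q4 in Section 9, Q5 in Sections 6.2 and 8). Also amend the statement that the date has only two uses, since Section 6.2 starts the look-back period from it.

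The cost is a few sentences, a few lines of code, and reliance on correct Q15 coding.

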## 10 STATISTICAL METHODOLOGY AND STATISTICAL ANALYSES

### 10.1 ANALYSIS SETS

All patients who meet all the inclusion criteria and none of the exclusion criteria will be included in the Full Analysis Set (FAS). All research objectives will be addressed via analysis of the FAS.

### 10.2 PRIMARY OBJECTIVE

Overall survival of all participants in the FAS will be tabulated at timepoints 6, 12, 18 and 24 months since the date of avelumab treatment initiation. Kaplan-Meier methods will be used to estimate rwOS, and survival curves will also be shown graphically for the 24-month duration of the follow-up time. The median and first and third quartiles of rwOS will be presented as the number of months, along with the 2-sided 95% confidence intervals calculated based on the Brookmeyer-Crowley method. The number of at-risk patients (ie, surviving and uncensored) will be shown at each timepoint under the survival curve. The estimated survival probability will also be presented at each timepoint, with confidence intervals generated using the log(-log) method with back-transformation to present results on an untransformed scale. The presentation of these results is illustrated in the table shells document (Table 1 and Figure 1).

### 10.3 SECONDARY OBJECTIVES

The secondary research objectives each involve descriptive analysis of the variables described in [Section 8](#), which includes clinical and demographic variables (objective 2), rwPFS (objective 3), treatment characteristics (objective 4), avelumab treatment patterns (objective 5), AEs attributed to avelumab (objective 6), and healthcare resource burden associated with avelumab (objective 7).

#### Analysis of time-to-event variables

Both secondary objective time-to-event endpoints will be analysed and reported following the same methods described above for the primary endpoint (rwOS) in [Section 10.2](#). This includes the analysis of time to progression (Objective 3; table shells Table 2.2 and Figure 2.1) and time to treatment discontinuation (Objective 5; table shells Table 2.4.2 and Figure 2.2).

#### Analysis of continuous variables

All continuous variables will be described using the following statistics: number of observations, mean, standard deviation, median, minimum, and maximum values, first and third quartile (Q1 and Q3). The mean, median, Q1 and Q3 will be displayed to one decimal place. The standard deviation will be displayed to two decimal places.

The number of AEs, number of hospitalisations, duration of hospitalisation, and number of Accident & Emergency visits will each be used to calculate a rate per patient per year of follow-up time. This will be calculated as the total number of incident events (or total number of days hospitalisation) recorded per patient during the follow-up time divided by the total follow-up time (time at risk) per patient in years. All rate variables will be presented in the same way as for the other continuous variables.

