Duration of treatment with avelumab	Treatment pattern from avelumab initiation	Between avelumab initiation and end of follow-up	Will be derived based on the date of avelumab initiation (index date) and the last date of avelumab treatment. The last day of avelumab treatment will be calculated based on the last recorded date of avelumab treatment received + 14 days. A gap of 30 consecutive days of no treatment with avelumab will be used to establish the last recorded date of avelumab treatment received.

Variable	Role	Time of measurement	Operational definition
Time interval between start of avelumab and start of 2L therapy	Treatment pattern from avelumab initiation	Between avelumab initiation and end of follow-up	Time interval will be derived using the dates of avelumab initiation and initiation of first regimen of 2L therapy. This parameter will be calculated only among patients who go on to receive 2L therapy after avelumab initiation

Number of patients who receive 2L therapy	Treatment pattern from avelumab initiation	Between avelumab initiation and end of follow-up	Number of patients who received 2L therapy after initiating avelumab
Number of patients who discontinue avelumab and start 2L therapy	Treatment pattern from avelumab initiation	Between avelumab initiation and end of follow-up	Number of patients who discontinue avelumab and subsequently receive 2L therapy
SACT regimen received as 2L therapy	Treatment pattern from avelumab initiation	Between avelumab initiation and end of follow-up	Among the number of patients receiving 2L therapy, unique SACT regimen reported as 2L therapy after avelumab initiation any time during follow-up
Number of SACT cycles received as 2L therapy	Treatment pattern from avelumab initiation	Between avelumab initiation and end of follow-up	Number of cycles received as 2L therapy after avelumab initiation
rwTTD from initiation of avelumab	Treatment pattern from avelumab initiation	Between avelumab initiation and end of follow-up	
Time between avelumab initiation until the earliest of:
 
 • Date of discontinuation (a gap of 30 days without treatment with avelumab will be used to establish a patient as having discontinued avelumab) • Having a subsequent systemic therapy regimen • Date of death from any cause 
See Table 1 for other censoring points

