9.2.3. Outcomes

Table 4. Outcome variables definitions

Variable	Role	Time of measurement	Operational definition

Primary objective: Estimation of overall survival			
rwOS	Patient outcome	From avelumab initiation to end of follow-up	Time between avelumab initiation until date of death from any cause See table 1 for other censor endpoints rwOS will be reported at 6-monthly intervals and at the end of the study.
Objective 2: Estimation of progression-free survival			
rwPFS	Patient outcome	From avelumab initiation to end of follow-up	Time between avelumab initiation until earliest of: 
 • Date of first progression • Date of death from any cause See Table 1 for other censor endpoints rwPFS will be reported at 6-monthly intervals and at the end of the study. Progression will be determined based on progression being referenced in a clinician and/or radiology report, as described by an electronic health record (EHR) study (14). A proxy for progression could also be established as the earliest of death or start of new SACT after avelumab initiation
Variable	Role	Time of measurement	Operational definition
Objective 5: To describe the adverse events attributed to avelumab in a real-world population			

Adverse events explicitly attributed to avelumab	Patient outcome	From avelumab initiation to end of follow-up	
Any AE with explicit attribution to avelumab as noted in the clinical records. Explicit attribution is not inferred by a temporal relationship between drug administration and an AE but must be based on a definite statement of causality by a healthcare provider linking drug administration to the AE.
 
 • AE diagnosis • Outcome of AE • Classification as either serious or non-serious AE 
 ◦ Results in hospitalisation or prolongation of hospitalisation ◦ Is life threatening ◦ Resulted in death ◦ Persistent or significant incapacity ◦ Congenital anomaly/birth defect in any offspring ◦ Other important medical event that may require medical or surgical intervention to avoid any of the above criteria • AEs discontinuation of avelumab • AEs leading to systemic steroid treatment
Objective 6: To describe real-world all-cause associated healthcare resource burden associated with avelumab therapy			
Variable	Role	Time of measurement	Operational definition

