### **Follow-up and Censoring**

The follow-up period for participants will be from the index date to the earliest date of:

- Death (as recorded in eCRF Q35)
- Loss to follow up (as recorded in eCRF Q36)
- 24 months after the index date

For each participant, the censoring date used for the time-to-event analyses will be the earliest date of loss to follow up or 24 months after the index date, as recorded on the eCRF. Note that death is treated as an event in the time-to-event analyses, therefore not used as a censor point. For the time-to-progression variable only, the start date of 2L SACT will be used as an additional censoring point. Specific definitions of events and

PFIZER CONFIDENTIAL

CT24-WI-GL03-RF03 0.2 *Non-Interventional Statistical Analysis Plan For Secondary Data Collection*  
*Study 01-Jun-2020*  
Page 15 of 34

censoring for each time-to-event variable individually are provided in the relevant section of the table in [Section 8](#).

For a subset of the variables, data will be collected from medical records prior to the index date and recorded retrospectively in the eCRF. This look-back period will cover the period for each patient from the date (inclusive) of their first UC diagnosis (relating to diagnosis at any stage; as recorded on the eCRF Q5) to the day before the index date (inclusive). This look-back period applies to some clinical and demographic characteristics to be described for Objective 2, as well as some pre-avelumab treatment patterns to be analysed for Objective 4 (see [Section 8](#) for full details of each variable and the time period to be used for data collection).

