Duration of avelumab treatment	Treatment patterns	From index date to end date of avelumab, or date of censoring (whichever is first)	Calculated as the number of days from the start date of avelumab treatment (eCRF Q25) to the latest date avelumab treatment was interrupted (eCRF Q27), inclusive of start and end dates. If the patient is censored before a stop date is recorded, the censor date will be used as a stop date. The eCRF allows for avelumab treatment pauses to be recorded; for the purposes of this variable, the pauses will be disregarded and the full duration will end on the most recent stop date recorded for eCRF Q27.
Time interval between start date of avelumab and start date of 2L therapy	Treatment patterns	From index date to start date of 2L therapy	
Calculated as the number of days from the start date of avelumab treatment (eCRF Q25) to the start date of the first regimen of 2L therapy (eCRF Q31), inclusive of the start and end dates of this period.
 
This will only be calculated for patients who report receiving 2L therapy after avelumab start date (in eCRF Q31).

PFIZER CONFIDENTIAL

CT24-WI-GL03-RF03 0.2 *Non-Interventional Statistical Analysis Plan For Secondary Data Collection*  
 Study 01-Jun-2020  
 Page 24 of 34

Number of patients who receive 2L therapy after avelumab start date	Treatment patterns	From index date to date of censoring	If any 2L therapy received after the start date of avelumab is reported in eCRF Q31 (any regimens reported vs. none reported)

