Adverse events	Patient outcome	From index date to date of censoring	The number of separate AEs recorded per patient (with explicit linkage in the medical notes to avelumab) will be calculated using data from eCRF Q39 (each reported event on the eCRF counts as a separate AE). This will be used to calculate the rate of events per patient per year of follow-up time
Objective 7: to describe healthcare resource burden associated with avelumab (table shell Table 2.6)			

PFIZER CONFIDENTIAL

CT24-WI-GL03-RF03 0.2 *Non-Interventional Statistical Analysis Plan For Secondary Data Collection*  
*Study 01-Jun-2020*  
 Page 26 of 34

Accident and Emergency visits	Healthcare resource burden indicator variable	From index date to date of censoring	The number of accident and emergency visits recorded per patient (each reported visit on the eCRF Q37 counts as a separate visit) will be used to calculate the rate of events per patient per year of follow-up time
Hospitalisations	Healthcare resource burden indicator variable	From index date to date of censoring	The number of hospital admissions recorded per patient (each reported visit on the eCRF Q38 counts as a separate visit) will be used to calculate the rate of events per patient per year of follow-up time
Duration of hospitalisation	Healthcare resource burden indicator variable	From index date to date of censoring	The total number of days duration of hospitalisation recorded per patient will be calculated as the sum of the duration of all separate hospitalisations reported per patient in eCRF Q38 (where the duration of each event is the number of days between the reported start and end date, inclusive of the start and end dates). This will then be used to calculate the number of days of hospitalisation per patient per year of follow-up time

PFIZER CONFIDENTIAL

CT24-WI-GL03-RF03 0.2 *Non-Interventional Statistical Analysis Plan For Secondary Data Collection*  
*Study 01-Jun-2020*  
 Page 27 of 34

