### **Further limitations**

All analyses are carried out on the FAS which includes all patients irrespective of the duration of avelumab treatment. As such, duration of avelumab treatment could confound the interpretation of some results, especially the efficacy endpoints (rwOS and rwPFS) and AEs, by inclusion of patients who may have started avelumab therapy but discontinued treatment after a short period. To account for this, the results will include descriptive statistics of treatment duration in the study population.

Research Objective 6 includes the descriptive analysis of AEs which are explicitly attributed to avelumab treatment, based on AEs being directly linked to avelumab in medical notes. Given that the data for analysis will be extracted from the standard medical records via eCRF and largely based on retrospective assessment of participants, it is unlikely that explicit linkage between AEs and avelumab will be consistently recorded. This means that descriptive statistics of AEs are likely to underestimate the numbers of AEs that are attributed to avelumab in a real-world setting.

The follow-up period for this study has been defined as 24 months from the date of avelumab treatment initiation, based on previous clinical trial data that median overall survival for patients receiving avelumab as 1L maintenance therapy in locally advanced or metastatic UC is 21.4 months (13). However, it is possible that this focus on a relatively short follow-up period will overlook longer-term outcomes (including, but not limited to, efficacy endpoints and safety events).

PFIZER CONFIDENTIAL

CT24-WI-GL03-RF03 0.2 *Non-Interventional Statistical Analysis Plan For Secondary Data Collection*  
*Study 01-Jun-2020*  
Page 31 of 34

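### AE and healthcare-use rates: add a pooled patient-year rate with a robust interval beside the equally weighted per-patient ratios

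*SAP*

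**What the plan says.** The SAP variable table (section 8) counts the AEs explicitly linked to avelumab for each patient and adds: "This will be used to calculate the rate of events per patient per year of follow-up time". The same construction is used for A&E visits, admissions and hospital days. Section 10.3 repeats it: each patient's total is "divided by the total follow-up time (time at risk) per patient in years. All rate variables will be presented in the same way" as other continuous variables, that is, by n, mean, SD, median, quartiles and range. No total over patients and no interval is mentioned. For time-to-event endpoints, by contrast, sections 10.2 and 10.3 plan 95% intervals.

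The denominator varies by design. SAP section 6.2 states: "The follow-up period for participants will be from the index date to the earliest date of" death, loss to follow-up or 24 months.

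Three neighbouring texts matter:
- Protocol 9.2.3, Table 4, sets the AE window as "From avelumab initiation to end of follow-up", so the SAP's choice of denominator agrees with the protocol. For healthcare use the same table asks for the mean and median number per patient; SAP section 8 specifies only rates.
- SAP section 10.5 accepts that "duration of avelumab treatment could confound the interpretation of some results", AEs among them, and responds with descriptive statistics of treatment duration.
- On when treatment ends, SAP section 8 says "the pauses will be disregarded and the full duration will end on the most recent stop date", while Protocol 9.2.2 uses "A gap of 30 consecutive days of no treatment with avelumab" and adds 14 days to the last recorded treatment date.

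**The concern.** A ratio with a very short denominator is mostly noise, yet here it counts as much as one based on 24 months. In a cohort where about half the patients are expected to die within the window, some short follow-ups are certain. The mean of the ratios is the planned statistic that looks most like events per patient-year, and a few early deaths could dominate it. A reader could build an interval from the reported n and SD, but it would be unreliable for the same reason. Together with the proportion of patients with any AE, these rates are the only AE results in the SAP text, and they are its only quantitative healthcare-use results.

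**Working it through.** **Inputs from the documents.** n = 100, follow-up capped at 24 months (SAP, Sample Size); survival 71.3% at 12 months and 48.0% at 24 months (Protocol 9.4, footnotes to Table 5).

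**Assumptions (the documents give no figures).** Event rate L per year; between-patient variance v of the relative rate; minimum follow-up 14 or 30 days; no loss to follow-up; share q of deaths preceded by a terminal admission.

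**1. The plan's own figures.** 100 × (1 − 0.713) = 28.7 deaths by 12 months (stated: 29) and 100 × (1 − 0.480) = 52 by 24 months (stated: more than 50). Clopper-Pearson intervals for 71/100 and 48/100 are 61.1–79.6% and 37.9–58.2%, as in Table 5. No AE or healthcare-use rate is stated, so there is none to reproduce.

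**2. Follow-up time.** A Weibull curve through both survival figures has shape ln(ln 0.480 / ln 0.713) / ln 2 = 1.118 and scale 31.65 months. (Its median is 22.8 months, not the cited 21.4; the two planning percentages determine it.) Survival at 3 months is 0.931, so 6.9 of 100 patients have under 3 months. Mean follow-up T is 1.447 years, or 145 patient-years in total. The patients with under 3 months hold 0.6–0.7% of that time but 7% of the weight in the mean.

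**3. One patient.** One 10-day admission over 20 days of follow-up is 365.25/20 = 18 admissions and 183 days per year; over 24 months it is 0.5 and 5. The first case alone adds 18.3/100 = 0.18 to the mean admission rate, but 1/145 = 0.007 to the pooled rate.

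**4. Precision when rates are constant and unrelated to survival.** Both statistics are then unbiased (the pooled rate up to a negligible ratio effect), with
- Var(mean of ratios) = (L·E[1/T] + v·L²)/n
- Var(pooled) = (L·E[T] + v·L²·E[T²]) / (n·E[T]²)

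For a 14-day minimum, E[T] = 1.447, E[1/T] = 1.565, E[T²] = 2.540; for 30 days, 1.448, 1.382, 2.540. With v = 0 the SE ratio is √(E[T]·E[1/T]) = √(1.447 × 1.565) = 1.50, or √(1.448 × 1.382) = 1.41. SE(mean)/SE(pooled), 14-day / 30-day minimum:

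| v | L = 0.5 | L = 1 | L = 3 | L = 5 |
|---|---|---|---|---|
| 0 | 1.50 / 1.41 | 1.50 / 1.41 | 1.50 / 1.41 | 1.50 / 1.41 |
| 1 | 1.26 / 1.20 | 1.16 / 1.12 | 1.03 / 1.01 | 0.99 / 0.97 |
| 2 | 1.16 / 1.12 | 1.07 / 1.04 | 0.97 / 0.96 | 0.95 / 0.94 |

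At L = 1 the SEs are 0.125 and 0.083 for v = 0, and 0.160 and 0.138 for v = 1 (14-day minimum). Break-even is v·L = (E[1/T] − 1/E[T]) / (E[T²]/E[T]² − 1) = 4.1 (14 days) or 3.3 (30 days). The ratio cannot fall below E[T]/√E[T²] = 0.91. Shorter minimum follow-up raises it: a piecewise-exponential curve with a one-day minimum gives 1.89 at v = 0.

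**5. When the two estimate different quantities.**
- *Events before death.* The mean targets L + q·E[1/T; death] and the pooled rate L + q·P(death)/E[T]. With L = 0.5, q = 0.3 and a 14-day minimum: 0.5 + 0.3 × 1.325 = 0.90 against 0.5 + 0.3 × 0.52/1.447 = 0.61. With 30 days: 0.84 against 0.61. For q of 0.3–0.5 and L of 0.5–1 the ratio of the two is 1.3–1.7 (14 days) or 1.2–1.6 (30 days).
- *Events soon after initiation.* If attributed AEs occur only on treatment, with assumed median treatment of 3.7, 6, 9 or 12 months, the ratio is 3.73/2.81 = 1.33, 2.56/2.11 = 1.21, 1.98/1.73 = 1.14 or 1.71/1.54 = 1.11, without any clustering before death.
- *High-rate patients dying sooner.* One simulated case (L = 1, v = 1) gives 1.00 against 0.78.

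**6. Which interval.** In simulation at L = 1, a plain Poisson 95% interval for the pooled rate covers 95% at v = 0, 76% at v = 1 and 64% at v = 2, and 30% for hospital days (v = 1, assumed mean stay 7 days). An interval based on between-patient variation covers 93–95%.

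**The case against.** These are secondary, descriptive outputs: section 10.3 opens with "The secondary research objectives each involve descriptive analysis of the variables described in" section 8, and the SAP makes no formal comparisons. Mean with SD and median with IQR follow Protocol 9.6.1. The planned median, quartiles and maximum expose outliers, and the median is robust to a few short follow-ups. The precision gain at low rates is modest beside a one-decimal display: at 0.5 events per year without heterogeneity the 95% half-widths are 1.96 × 0.088 = 0.17 and 1.96 × 0.059 = 0.12. The table shells are a separate document and may contain totals. Protocol 9.6 lets the SAP modify the protocol's plans, so replacing counts by rates is permitted.

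Most of this stands, and it limits the point to a reporting improvement. Two replies remain. The median does not replace a rate when events are sparse: at 0.5 per year without heterogeneity the study median is exactly 0 in 57–58% of simulated studies. And descriptive status does not explain the missing interval, since the equally descriptive time-to-event endpoints have one.

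A reader might infer that the pooled rate is always more precise. It is not: the advantage shrinks with heterogeneity and reverses slightly once v·L passes about 3 to 4. A reader might also infer that the mean exceeds the pooled rate only when events cluster before death; step 5 shows two other routes.

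**Conclusion.** The point holds as a cheap improvement of low severity. The SAP text summarises these rates only as equally weighted per-patient ratios without an interval, and the mean rate is sensitive to the roughly 7 in 100 patients expected to have under 3 months of follow-up. That count rests on the protocol's survival figures. The SE ratios (1.4–1.5 without heterogeneity, 1.0–1.3 with moderate heterogeneity, about 0.94–0.98 for frequent events with strong heterogeneity) and the contrast of 0.90 with 0.61 rest on assumed rates, heterogeneity, clustering and minimum follow-up.

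Two stronger readings are not supported. The planned mean is not wrong, nor must the pooled rate become the main result: where rates depend on time or survival the two answer different questions, and the documents do not say which is wanted. Nor is the AE denominator an error because follow-up continues after avelumab stops: the rate is labelled per year of follow-up, matches Protocol Table 4, and the SAP discloses the limitation. The primary analysis of rwOS is untouched.

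**What to change.** In SAP section 10.3 and the table shells:
- Beside the per-patient summaries, report total events (or hospital days), total patient-years and their ratio, with a 95% interval from a patient-level bootstrap or another method robust to between-patient variation, not plain Poisson.
- State that the pooled rate and the mean of patient rates are different summaries and need not agree.
- For healthcare use, also report the mean and median number per patient that Protocol Table 4 specifies; these are the numerators already being derived.

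Optionally, add an AE rate per patient-year of avelumab exposure as a supplement, with the same risk window for numerator and denominator. The stop-date and pause rules in SAP section 8 and Protocol 9.2.2 must first be reconciled, since they define exposure differently.

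The cost is SAP and shell wording, some programming and a few more table rows. No new data are needed: eCRF Q25, Q27 and Q35–Q39 already hold the dates and events.
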